2 RATIONALE

[figure not shown]
Our randomized controlled trial aims to establish if screening results in a clinically meaningful and cost-effective reduction in Ng/Ct incidence in MSM PrEP cohorts that could outweigh the increased risk of AMR development it confers. We considered conducting a cluster randomized controlled trial to evaluate if screening is associated with a reduction in Ng/Ct prevalence at population level. The cost of such a study would be very high [31] and evidence from behavioural surveys and HIV/STI phylogeny in Belgian MSM indicates a very high rate of sexual mixing between populations in different Belgian towns [32-35]. As a result, the probability of effect-contamination between randomized centres would be high. These factors are not unique to Belgium and consequently a number of authors have concluded that this type of community level RCT is unlikely to ever take place [23, 31].

Furthermore, as already noted, the available evidence from ecological analyses, our systematic review of observational data of the effect of Ng/Ct screening on prevalence as well as evidence from modelling evaluations all suggest that screening is unlikely to have a noticeable effect on the prevalence of Ng/Ct at a population level in contemporary PrEP cohorts.

This still leaves the important clinical question of whether or not screening at an individual level is able to reduce the risk of acquiring Ng and Ct. Even if 3x3 screening has no effect on Ng/Ct prevalence at a population level, it could reduce prevalence at an individual level. This is illustrated in Figure 4 which contrasts schematically the impact of Ng screening on two populations – one with a densely connected sexual network and one with a somewhat lower network connectivity. Starting with the lower connectivity population (lower panel), if 8% of the network is screened weekly (corresponding to 100% coverage with 3 monthly screening) and this includes individual 'a', then screening in this setting is likely to reduce the probability that 'a' will be infected with Ng (green squares) by the time of his second screening (week 12) via two mechanisms. Firstly, screening will result in 'a's Ng being detected and eliminated which will prevent it spreading to 'a's uninfected partner ('b') which will in turn reduce the probability that 'a' will be infected with Ng at his next visit. Secondly, if 'a' is found to test positive for Ng then his partners will be invited for testing which could result in his Ng-infected-partner ('c') being treated for Ng which would further reduce the probability that 'a' would be infected with Ng at subsequent visits.

Alternatively, the local sexual network could be so dense (upper panel) that 3x3 screening may have little or no impact on prevalence. In this scenario, the Ng from 'd' and one of his infected partners ('e') is eliminated by screening at baseline but his local sexual network is so dense that he is rapidly re-infected with Ng. Screening in this setting has little probability of reducing the probability of incident Ng infection for individual 'd' or others in this sexual network.

Figure 4. An illustration of how Ng screening in a lower connectivity sexual network may reduce the probability of incident Ng for an individual 'a', whereas it has little or no effect in a high connectivity network. See text for details. (Ng infected individuals- green squares; Uninfected individuals- grey squares; Edges between squares represent sexual relationships).

These considerations have resulted in the current proposal where we plan to conduct an individual level RCT to assess if 3x3 screening for Ng/Ct is associated with a reduced incidence of these infections after 12 months screening versus no screening. One of the secondary outcomes will be assessing the efficacy of screening in those with relatively lower risk behavior (defined as 4 or fewer partners per 3 month period; represented by the lower connectivity network in Figure 3).

We are aware that participants in the no-screening arm would not be receiving the standard of care prescribed according to the Belgian PrEP guidelines. These PrEP guidelines were however developed by the Belgian Research on AIDS and HIV Consortium (BREACH) and discussions within BREACH informed by local research have led to serious doubts about the merit of 3x3 Ng/Ct screening [4, 6, 12, 14, 25]. For the reasons outlined above, we are concerned that our current guidelines may even be doing more harm than good. As a result, the 2018 annual general meeting of BREACH endorsed an RCT to evaluate the benefits and harms of 3x3 screening in Belgium PrEP cohorts. This study is thus the product of local efforts to produce evidence to help establish what the best standard of care should be vis-à-vis screening for Ng and Ct in PrEP recipients.

Phase II - cessation of Ng/CT screening in MSM

If the GonoScreen Study finds that screening is not associated with a reduced incidence of Ng plus Ct infections, then a second phase of the study is foreseen (separate from the current study proposal). In this second phase, we will present the GonoScreen Study results to BREACH with the recommendation that we cease screening MSM (PrEP recipients and other MSM) whilst closely monitoring the impact this has on incident STIs in a yet to be agreed upon strategy.

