4 OBJECTIVES AND ENDPOINTS / OUTCOME MEASURES

Study hypothesis

The study hypothesis is that 3x3 screening in MSM PrEP recipients is not associated with a reduction in the incidence of Ng plus Ct infections over 12 months.

Table 1. PICO Table

Population	All MSM participants aged 18 or older, enrolled to receive HIV PrEP at the Institute of Tropical Medicine, Antwerp (ITM), Hôpital Saint-Pierre (HSP), University Hospital of Gent (UZG), Erasmus Hospital (EH) and Liège University Hospital (CHU) who consented to participate in the trial. Participants must report having had sex with another man in the prior 12 months.
Intervention	Participants in the intervention arm will not be screened for Ng/Ct for a period of 12 months, in reference to the routine practice of screening (and treating screening-positive) participants every 3 months (see 'Comparator'). More specifically, participants in the intervention arm will have 3 site (urethra, pharynx and rectum) sampling performed every 3 months but these testing results will only be reported at the end of the 12 month period. Those testing Ng and/or Ct positive at their last visit in the 12 month period will be recalled and offered treatment even in the case of asymptomatic infection (cfr. current routine care). All individuals with symptomatic infections will be treated according to current best practice guidelines, including contact tracing. Participants in the intervention arm will also be treated if contacted via contact tracing.
Comparator	3x3 screening. For a period of 12 months, all participants will be screened for Ng/Ct at three sites (urethra, pharynx and rectum) every three months according to current Belgian guidelines. If they test positive they will be recalled for treatment for Ng/Ct and contact tracing.
Outcome	
Primary outcome:
 
Incidence rate of Ng plus Ct detected at any site whilst individuals are not screened vs. screened
 
Secondary outcomes:
 
 • Cumulative antimicrobial exposure (ceftriaxone/azithromycin/doxycycline) • Incidence of symptomatic Ng plus Ct • Incidence of syphilis • Incidence of HIV • Cost effectiveness of 3x3 screening vs. no screening • Variations in PrEP users' perceptions towards STI screening (only for ITM subjects)

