- “By screening I am protecting my partner”
- “By screening I am protecting myself from symptomatic Ng/Ct”

As already noted above, we do not know if screening has these beneficial effects. In our discussions with PrEP recipients it has emerged that many believe that we screen for Ng/Ct based on good evidence of efficacy in terms of these two parameters. They typically express considerable surprise when we explain this is not the case. This creates a significant problem for health economic evaluations that compare quality of life in screening vs. non screening arms. If participants falsely believe that screening is highly efficacious then it is possible that a quality of life (QoL) assessment in our study would reveal a higher QoL in those screened vs non-screened. This could occur despite the study finding no difference in symptomatic Ng/Ct and onward transmissions (as assessed in phase 2).

If the study was then repeated with the same individuals but with this new information given to them (that screening does not reduce transmission or symptomatic disease) then those screened may now report a lower QoL than those in the non-screening arm. This could be explained by this individual no longer having the two cognitions and instead having the cognitions:

- “Screening will not reduce my partners probability of acquiring Ng/Ct”
- “Screening will not reduce my probability of getting symptomatic Ng/Ct”

In this new scenario, QoL may be further reduced in those screened due to the money and time spent on screening as well as side effects from and perceptions related to the adverse effects of antibiotics.

These considerations lead us to conclude that the key information we require at this stage is the efficacy of Ng/Ct screening and that including QoL assessments in our study design would not be appropriate.

In the event of us finding non-inferiority in our primary outcome, we will conduct an analysis to assess what the cost savings of the cessation of screening for Ng/Ct in MSM in Belgium would be.

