If we find that no-screening is non-inferior to 3x3 screening, we will be able to recommend the cessation of Ng/Ct screening in the approximately 1526 individuals in PrEP follow up in Belgium and save these direct costs. A reasonable case could also be made based on these findings that Ng/Ct screening could also be stopped in MSM more generally. Since local and European guidelines recommend 3 site screening for all sexually active MSM from 3 to 12 monthly and there are an estimated 148 081 MSM in Belgium this could result in considerable cost saving to the health care system [52]. Furthermore, the number of individuals on PrEP is expected to continue to grow to cover approximately 20% of the MSM population [53].

We also plan to model the effects of stopping screening on the selection of antimicrobial resistance in Belgium. The major motivation and the major anticipated utility of the trial is the reduction of antibiotic use in a key population where antimicrobial resistance has frequently emerged [54]. By reducing antibiotic usage, we aim to reduce the probability of the emergence of antimicrobial resistance in Ng as well as a range of other STIs and other infections. Whilst it is difficult to attach a cost saving value to an intervention that prevents the emergence of highly resistant and untreatable infections such as Ng, it is important to do so. The O'Neill Report, for example, predicted that infections due to antimicrobial resistant bacteria will result worldwide in 300 million deaths and a cumulative cost of \$100.2 trillion by 2050 if we continue on the current

trajectory [55]. We will attempt to quantify these long-term effects for the Belgian population by adapting our model of Ng transmission in MSM in Belgium [56] to model the probability of emergence of resistance given various intensities of antimicrobial consumption/screening intensity.

If we find that screening is associated with a reduction in the incidence of Ng plus Ct, we will conduct cost-effectiveness evaluations such as calculating the cost per averted infection.

We plan to collect the costs relating to laboratory testing, price of antimicrobial therapy and administration and costs of consultations from standard sources such as RIZIV/INAMI reimbursement schema and BCFI.

Table 3: Major costs and benefits of 3x3 screening in MSM

Costs	Benefits
Direct	
Cost of 3 site screening (molecular testing)	Possible reduced risk of symptomatic Ng/Ct (individual level benefit)

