Interim analyses are planned at two time points: once 50% and 100% of all study recruits have passed their 6 month visit. For the first interim analysis, data is used of the first 507 enrolled participants (i.e. ordered by randomization date) until 6 months follow-up. For the second analysis, data is used of all enrolled participants until 6 months follow-up. The goal of the interim analyses (at both time points) is to estimate the incidence rate ratio of symptomatic Ng plus CT. Estimates will be based on a Poisson regression model (or a negative binomial regression model if there is overdispersion) with number of symptomatic diagnoses as dependent variable, arm and hospital as independent variables and log(number of visits) as offset. This model will provide estimates of the incidence rate in each arm and the incidence rate ratio (no screening versus screening), together with 95% confidence interval. Visits with missing data on the diagnosis of Ng or Ct, will be excluded from the calculation of the incidence rate (excluded both from numerator and denominator).

7. Analysis of main efficacy outcomes: Incidence of Ng plus Ct

In each arm, the incidence of Ng plus Ct will be estimated together with 95% confidence interval. Estimates will be based on a Poisson regression model (or a negative binomial regression model if there is overdispersion) with number of diagnoses as dependent variable, arm and hospital as independent variables, and log(number of visits) as offset. This model will also provide an estimate of the log incidence rate ratio (no screening versus screening), together with 95% confidence interval. The 'no screening' arm is proven to be non-inferior if the upper limit of the 95% confidence interval is lower than $\log(1.25)$.

Visits with missing data on the diagnosis of Ng or Ct, will be excluded from the calculation of the incidence rate (excluded both from numerator and denominator).

In a sensitivity analysis, the numerator of the primary endpoint will only include diagnoses if there was a negative test result at the prior visit.

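### The protocol gives two inconsistent conditions for recommending that screening stop, and does not say what follows an inconclusive result

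*Protocol*

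**What the plan says.** Two conditions lead to the same recommendation.

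- **Without a margin.** The Phase II paragraph of protocol section 2 begins "If the GonoScreen Study finds that screening is not associated with a reduced incidence of Ng plus Ct infections". In that event a separate second phase is foreseen, in which "we will present the GonoScreen Study results to BREACH with the recommendation that we cease screening MSM (PrEP recipients and other MSM", with close monitoring under a strategy still to be agreed. The hypothesis in protocol section 4 has the same form: "3x3 screening in MSM PrEP recipients is not associated with a reduction in the incidence of Ng plus Ct infections over 12 months". Sections 9.2 and 14.1 also describe the trial's question as whether screening is associated with fewer infections.
- **With a margin.** Protocol section 11.4 says "If we find that no-screening is non-inferior to 3x3 screening, we will be able to recommend the cessation of Ng/Ct screening", and makes the cost-savings analysis depend on the same result: "In the event of us finding non-inferiority in our primary outcome, we will conduct an analysis to assess what the cost savings". The primary objective (section 4.1) is non-inferiority. Protocol sections 11.1 and 11.3.2 and SAP section 7 give the rule: "The 'no screening' arm is proven to be non-inferior if the upper limit of the 95% confidence interval is lower than" log(1.25).

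Section 11.4 has one more branch: "If we find that screening is associated with a reduction in the incidence of Ng plus Ct, we will conduct cost-effectiveness evaluations". No section says what follows when neither non-inferiority nor a reduction is shown.

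**The concern.** A finding of no association and a finding of non-inferiority are different results. If the first is taken to mean that the interval does not exclude a ratio of 1, it is easier to meet when the trial is less precise. The second is harder to meet when the trial is less precise, and that is the reason for having a margin. Under the Phase II wording, a trial that fails its own primary test could still support advice to stop screening in PrEP users and other MSM. Leaving two wordings in place also allows the choice between them to be made after the results are known.

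**Working it through.** **Inputs (protocol 11.1 and 8.3).** Baseline mix 79% / 18% / 3% with 0 / 1 / 2 diagnoses; mean diagnoses per follow-up visit 0.15 / 0.28 / 0.34 in those groups; 95% of participants with 4 visits and 5% with 3; margin 1.25; two-sided 95% interval; true ratio 1.00; 912 evaluable, allocated 1:1; 10% dropout.

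**Reproducing the plan's figures.**
- Mean per visit = 0.79 × 0.15 + 0.18 × 0.28 + 0.03 × 0.34 = 0.1791. Over 4 visits this is 0.716 (stated: 0.72).
- Mean visits = 0.95 × 4 + 0.05 × 3 = 3.95. Expected diagnoses per arm = 456 × 3.95 × 0.1791 = 322.6.
- SE of the log ratio at a true ratio of 1.00 = √(2/322.6) = 0.0787.
- Power = Φ(ln 1.25/0.0787 − 1.96) = 80.9%. The closed-form N for 80% power is 892, against 912 stated from simulation. A simulation from the protocol's visit table (4,000 runs) also gives 80.9%.
- 912/0.90 = 1013.3, rounded up to 1014 (stated: 1014).

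**Two rules compared.** Rule A is the SAP rule: upper 95% limit below 1.25. Rule B is the assumed ordinary reading of Phase II, no significant reduction: lower 95% limit at or below 1. For a true ratio R:
- SE(R) = √(1/322.6 + 1/(322.6 R))
- P(A) = Φ((ln 1.25 − ln R)/SE − 1.96)
- P(B) = Φ(1.96 − ln R/SE)
- P(inconclusive) = P(B) − P(A)

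| True ratio | Rule A | Rule B | Inconclusive |
|---|---|---|---|
| 1.00 | 80.9% | 97.5% | 16.6% |
| 1.10 | 38.3% | 76.5% | 38.2% |
| 1.15 | 19.4% | 54.9% | 35.6% |
| 1.20 | 7.8% | 32.3% | 24.5% |
| 1.25 | 2.5% | 15.2% | 12.7% |
| 1.30 | 0.6% | 5.7% | 5.0% |

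Only 1.00 and 1.25 come from the documents; the other ratios are assumptions that show the range. At 1.25 the SE is √(1/322.6 + 1/403.2) = 0.0747, so P(B) = Φ(1.96 − 0.2231/0.0747) = 15.2%. The simulation at 1.25 gives 15.9% for rule B and 3.3% for rule A.

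**An inconclusive result.** With SE 0.0787, a result is inconclusive when the observed ratio lies between about 1.07 and 1.17. An observed 1.12 gives exp(0.1133 ± 1.96 × 0.0787) = 0.96 to 1.31. This fails rule A, meets rule B, and falls in neither branch of section 11.4.

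**Fewer infections.** With half the expected diagnoses, the SE at 1.25 becomes 0.0747 × √2 = 0.1056. P(B) = Φ(1.96 − 0.2231/0.1056) = 44%, while P(A) stays at 2.5%.

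**The case against.** The strongest reply is that the Phase II sentence is loose wording for non-inferiority. It speaks of what the study finds, and the only favourable finding that the plan defines is non-inferiority. Section 2 states the aim as a clinically meaningful reduction, which fits a margin, and section 4.3.1 words the favourable conclusion as non-inferiority. The lower-limit test used above as rule B appears nowhere in the documents. This stands as a possible reading, and it is why the calculation is conditional. It does not remove the inconsistency, because the wording recurs in the hypothesis and nothing in the protocol says that the two phrasings mean the same.

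The documents do not support several stronger readings:
- A reader might infer that absence of association is the only cessation rule. Section 11.4 contradicts this.
- A reader might infer that an inconclusive trial would stop screening automatically. Section 2 provides only for a recommendation to BREACH, in a separate phase with monitoring.
- A reader who applies the SE implied by 80% power under no difference (0.080) at a ratio of 1.25 would get about 20%, or eight times 2.5%. At that ratio the no-screening arm has more events, so the figure is about 15%.
- A reader might worry about a result that shows both non-inferiority and a reduction. An interval wholly between 1 and 1.25 needs an SE below ln 1.25/(2 × 1.96) = 0.0569, or about 617 diagnoses per arm. The plan expects about 323.

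It is also true that the objective, sample size, protocol analysis and SAP agree with one another. The primary analysis and its error rate are unaffected.

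**Conclusion.** The inconsistency is real and worth correcting. The Phase II trigger and the hypothesis carry no margin, section 11.4 relies on non-inferiority, and an inconclusive result has no stated consequence. That result is not rare: about 17% likely if there is no true difference, and about 38% at an assumed true ratio of 1.10.

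If the Phase II wording is read as no significant reduction, the chance that its condition is met at the margin is about six times the SAP's 2.5% (15.2/2.5 = 6.1; about five times in the simulation), and it grows as precision falls. These figures assume that reading, the protocol's event rates, 912 evaluable participants and Poisson variance. Overdispersion beyond the visit table would make inconclusive results more likely. If the wording was meant as non-inferiority, only the wording and the missing inconclusive case need repair.

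**What to change.** 1. Protocol section 2, Phase II: state the trigger as the upper limit of the 95% confidence interval of the primary rate ratio being below 1.25, with a reference to SAP section 7.
2. Protocol section 4: restate the hypothesis as non-inferiority of no screening to 3x3 screening, with a rate ratio margin of 1.25.
3. Protocol sections 2 and 11.4: state that an upper limit of 1.25 or more with an interval that includes 1 is inconclusive and supports no cessation recommendation.

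The cost is wording in three protocol sections. Data collection, sample size and analysis stay as they are. The one downside is that the sponsor gives up the option of recommending cessation after an inconclusive result.

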7.1. Subgroup analyses

We will conduct a prespecified subgroup analysis to assess the incidence of Ng plus Ct in screening vs. non-screening arms in participants with lower-risk behavior. An individual with lower-risk behavior is defined a priori as those individuals who report 4 or fewer partners per 3-month period in all 5 relevant 3 month periods with data available. These periods are the 3-months prior to study enrollment as well as the four 3 month periods during study follow up. The analysis will be analogous to the analysis of the primary objective, but restricted to participants with lower-risk behavior.

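### An overall result in PrEP users may be carried to other MSM, yet the only risk-group analysis covers the lower-risk subset alone and defines it largely by behaviour after randomisation

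*Protocol*

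**What the plan says.** **Population.** Protocol section 4 (Table 1) and section 7.1 limit enrolment to people in PrEP follow-up at five centres.

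**Use of the result.** Under the Phase II heading of section 2, a finding that screening does not lower incidence would be taken to the Belgian HIV consortium "with the recommendation that we cease screening MSM (PrEP recipients and other MSM"). The text adds that "a second phase of the study is foreseen (separate from the current study proposal") and that cessation would proceed "whilst closely monitoring the impact this has on incident STIs in a yet to be agreed upon strategy". Section 11.4 returns to the idea: "A reasonable case could also be made based on these findings that Ng/Ct screening could also be stopped in MSM more generally". It sets about 1526 people on PrEP beside an estimated 148 081 MSM in Belgium.

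**Expected effect by network.** Section 2 contrasts two schematic networks. In the sparser one, "screening in this setting is likely to reduce the probability that 'a' will be infected with Ng"; in the dense one it expects little effect. The Figure 4 caption repeats that "Ng screening in a lower connectivity sexual network may reduce the probability of incident Ng for an individual". The Figure 3 legend in section 1 describes a typical PrEP cohort as highly connected.

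**Risk-group analysis.** Protocol section 11.3.2 and SAP 7.1 define lower risk as at most 4 partners in each of five 3-month periods: one before enrolment and four during follow-up. SAP 7.1 takes this over the periods with data available. On the model it says: "The analysis will be analogous to the analysis of the primary objective, but restricted to participants with lower-risk behavior". Neither document plans a higher-risk estimate or an arm-by-risk term, and neither ties the Phase II recommendation to the subgroup result.

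**The concern.** The rationale proposes that network density modifies the effect of screening. The plan does not estimate that modification, and it foresees carrying the pooled result beyond the enrolled population. If the hypothesis is right, a pooled ratio close to 1 could combine no effect in one group with a real effect in the other.

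The planned subset analysis is weak evidence on this for two reasons.

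- It yields a single within-group ratio. A wide interval there neither supports nor contradicts a difference between risk groups.
- Membership depends on partner counts reported after randomisation. Section 8.4 states that the trial is unblinded and that participants can work out their arm. Section 3 and Table 3 of section 11.4 both say that screening may increase risk behaviour. If so, arm affects who qualifies as lower risk, and the comparison within that subset is no longer protected by randomisation.

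At stake is how far the recommendation can be supported. The primary comparison in PrEP users is not affected.

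**Working it through.** **1. Reproduce the plan's sample size (Protocol 11.1).**
- Mean diagnoses per visit: 0.79 × 0.15 + 0.18 × 0.28 + 0.03 × 0.34 = 0.1791. Over 4 visits this is 0.716 (stated 0.72).
- Mean visits: 0.95 × 4 + 0.05 × 3 = 3.95.
- Events per arm with 912/2 = 456 participants: 456 × 0.1791 × 3.95 = 322.6.
- SE of the log rate ratio at a true ratio of 1: √(2/322.6) = 0.0787.
- Power: Φ(ln 1.25/0.0787 − 1.96) = Φ(0.87) = 0.81. A simulation from the plan's table gives 80.7% (stated 80%).
- 912/0.9 = 1013.3, rounded up to 1014, as stated.

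The stated size reproduces. It covers the overall comparison only.

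**2. Assumptions for the illustration.** The documents give neither the size nor the event rate of the lower-risk group. I assume that it supplies a share s = 10%, 20% or 30% of diagnoses, that its true ratio (no screening versus screening) is 1.5, and that the ratio in the others is 1.0. No overdispersion is assumed; with it, the subgroup intervals would be wider and the probabilities in the table lower.

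**3. Formulas.**
- Overall ratio: R = 1 + 0.5s.
- P(non-inferiority declared overall) = Φ((ln 1.25 − ln R)/0.0787 − 1.96).
- Subgroup events per arm: e = 322.6 × s.
- Subgroup upper 95% limit at an observed ratio of 1: exp(1.96 × √(2/e)).
- P(subgroup limit below 1.25) at a true ratio of 1: Φ(ln 1.25/√(2/e) − 1.96).
- Interaction SE: √(2/e + 2/(322.6 − e)), with two-sided 5% power.

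**4. Results.**

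| Share s | Overall ratio | P(overall non-inferiority) | Subgroup events per arm | Subgroup upper limit at ratio 1 | P(limit < 1.25) at true ratio 1 | Interaction power, ratio of ratios 1.25 / 1.5 |
|---|---|---|---|---|---|---|
| 10% | 1.05 | 60% | 32 | 1.63 | 14% | 14% / 34% |
| 20% | 1.10 | 37% | 65 | 1.41 | 24% | 21% / 54% |
| 30% | 1.15 | 18% | 97 | 1.33 | 34% | 26% / 66% |

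Example, s = 10%: (0.2231 − 0.0488)/0.0787 − 1.96 = 0.25, and Φ(0.25) = 0.60. Allowing for the slightly larger number of events in the no-screening arm moves the three probabilities to 61%, 38% and 19%.

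**5. Wider assumptions.** Let the lower-risk group be 10–50% of participants, with a diagnosis rate 0.6 to 1.0 times that of the others. Power for non-inferiority within the group is then 10–52% at a true ratio of 1. Power for a ratio of rate ratios of 1.25 is 10–29%. The smallest ratio of rate ratios detectable with 80% power is about 1.55 to 2.5.

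**6. Post-randomisation membership.** Four of the five defining periods follow randomisation. The documents give no data from which to size the resulting selection, so none is computed. Partner number in the 3 months before enrolment is already a baseline item (Protocol 8.6), so a definition that arm cannot influence is available.

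**The case against.** Much of the case on the other side stands, and it rules out several stronger readings.

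- **A reader might infer that the protocol itself calls other MSM the less connected men.** It does not. Section 2 contrasts two schematic networks and then equates the sparser one with trial participants reporting few partners. Placing other MSM there is a plausible inference from the description of PrEP cohorts, but it is not stated.
- **A reader might infer that the subgroup is the only evidence on other MSM.** Section 1 also cites a systematic review of observational studies in MSM, ecological comparisons that draw on a European survey of 180 000 MSM, and a model showing a minimal effect on prevalence in Belgian MSM. It reports a model with the opposite conclusion too. This evidence can be debated, but it exists. It is observational, ecological or modelled, and section 2 says that the question of individual benefit remains open.
- **A reader might infer that this trial would itself end screening in other MSM.** Phase II is a separate step, put to a consortium as a recommendation and with monitoring, although the monitoring strategy is not yet agreed. Section 11.4 says only that a case could be made.
- **Masking is not certain.** At shares of 20–30%, overall non-inferiority is declared in fewer than half of trials. Nothing in the documents shows that higher-risk men supply most diagnoses.
- **A lower-risk analysis is prespecified** and will give a rate ratio with an interval. That meets part of the point.

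It is also tempting to allow extension only if the lower-risk upper limit is below 1.25. Under shares of 10–30% that would be met about 14–34% of the time even if screening did nothing, so it would usually block extension for lack of precision. I do not recommend it.

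What remains is that no contrast between risk groups is planned, the subset is defined partly after randomisation, and the recommendation is not linked to either.

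**Conclusion.** The concern holds in a limited form. The plan foresees taking an overall null result in PrEP users to a wider population, while its own rationale proposes that the effect differs by network density and its analysis does not estimate that difference. Under the assumed shares and effect, a true 50% increase in the lower-risk group would coexist with a declared overall non-inferiority in 60% (10% share) down to 18% (30% share) of trials. The subset analysis, with 32–97 events per arm, would have an upper limit of 1.63–1.33 even at a ratio of 1. These figures illustrate the risk; they are not predictions, because both inputs are mine.

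The firmer part needs no assumed numbers: membership of the subset can be affected by arm, and there is neither a second stratum nor an interaction estimate. Both can be put right with data already collected. The primary inference in PrEP users stands.

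**What to change.** **SAP 7.1 and Protocol 11.3.2.**
- Define the risk group by partners in the 3 months before enrolment (4 or fewer versus more).
- Add risk group and arm by risk group to the full primary model.
- Report the rate ratio in each stratum and the interaction ratio, with 95% intervals, as estimates and not as a pass/fail test.
- Keep the five-period definition as a supplementary analysis, noting that membership is partly determined after randomisation.

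**Protocol section 2 (Phase II) and section 11.4.** State that the primary result applies to PrEP recipients. State also that any extension to other MSM will be presented with the two stratum estimates and their intervals. Do not add a 1.25 criterion for the lower-risk stratum.

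**Cost.** The change needs wording in four places, and risk group with its interaction with arm in one model. It needs no new data, visits or participants, and the primary analysis is unchanged. The interaction estimate will be imprecise, with about 10–29% power for a ratio of rate ratios of 1.25 under the assumptions above. A single baseline period describes continuing risk less fully than five periods, which is why the longer definition is kept as a supplement. The headline recommendation becomes narrower.
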